## **7.9 Adjustments for Multiplicity**

The secondary endpoint will only be tested if the primary endpoints are met, using the following hierarchical testing structure:

1. Test the co-primary endpoints, each at  $\alpha=0.025$
2. If fail to reject  $H_0: p_s \geq 0.12$  or fail to reject  $H_0: p_E \leq 0.50$ , then testing is stopped.
3. If reject  $H_0: p_s \geq 0.12$  and reject  $H_0: p_E \leq 0.50$ , then continue to conduct the test of secondary endpoint for  $H_0: P12m \leq 0.50$  at  $\alpha=0.025$ .

## **7.10 Analyses of Secondary Effectiveness Endpoint**

If success is achieved in both the primary safety and acute effectiveness endpoints, then the secondary effectiveness endpoint will be evaluated using the exact test for a binomial proportion at a one-sided significance level of 2.5%. If the lower bound of the exact two-sided 95% confidence interval of the 12-Month effectiveness success rate is greater than the performance goal of 50%, the study will be considered to have demonstrated long-term (12-Month) effectiveness. Testing of the hypothesis for the secondary effectiveness endpoint ensures family-wise error rate is controlled at a 2.5% level after the success of the primary endpoints is met.

The secondary effectiveness endpoint will be performed in the PP analysis set when all subjects have completed their 12-month follow-up. The analyses results will be reported in the final CSR

The following additional analysis will be performed for the secondary effectiveness endpoint based on 12-month follow-up data:

- **Sensitivity to Analysis Set**

The secondary effectiveness endpoint will be analyzed in the mITT analysis set as a sensitivity analysis.

- **Kaplan-Meier Analysis**

Kaplan-Meier estimates and plots will be used to characterize the time to first failure event of the secondary effectiveness endpoint, including acute effectiveness failure, recurrence of documented symptomatic/asymptomatic AF/AT/AFL episodes during evaluation period. The probability of freedom from the secondary effectiveness endpoint failure at each follow-up timepoint post blanking will be presented. The KM analysis will be performed in the PP and mITT analysis sets.

- **Best-case Scenario**

The point estimate for freedom from secondary effectiveness failure will be estimated by treating subjects with missing secondary effectiveness outcomes as free from secondary effectiveness events.

- **Worst-case Scenario**

The point estimate for freedom from secondary effectiveness failure will be estimated by treating subjects with missing secondary effectiveness outcomes as failures.

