The planned performance goal for 12-month effectiveness is 50%, based on the minimum chronic acceptable success rate for paroxysmal AF at 12-month follow-up as recommended in the 2017 HRS/EHRA/ECAS Expert Consensus Statement³⁸ on Catheter and Surgical Ablation of AF. Data from large multicenter pre- and post-market clinical trials of AF ablation devices which were published between 2014 to 2019 were reviewed as a first step to deriving the performance goal for the safety endpoint. A meta-analysis approach was taken to estimate the average composite endpoint rate. The following trials were reviewed: Fire & Ice³⁹, Heartlight^{40, 43}, TOCCASTAR⁴¹, ZERO-AF⁴⁴, and SMART-AF⁴². These trials are representative of different catheter designs and energy sources. Since the definition of the safety composite varies across the studies reviewed, individual complication rates were reviewed and utilized to derive composite rates from each trial that are more closely aligned with the proposed primary safety composite endpoint definition. This clinical investigation is intended to characterize safety and effectiveness of the investigational devices in scope. The study is not designed to include a comparator/control group since it is not intended to prove superiority.

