19.4.6.1 Handling of Missing Data

- For the final primary safety analysis, if a subject does not have full 12 months of follow-up and the subject has had a PAE at any time during the follow-up, then the subject will be considered an event. If a subject does not have 12 months of follow-up but has at least 3 months of follow-up, then their last observed status will be carried forward for the 12-month safety endpoint as a conservative proxy. If a subject does not have at least 3 months of follow-up for the primary safety endpoint, then this subject will be excluded from the final primary safety analysis.

- For the final secondary effectiveness analysis, if a subject has an effectiveness failure at any time during the evaluation period, then the subject will be considered having an event. Subjects without an effectiveness failure who do not have full 12 months of follow-up will be excluded from the final effectiveness analysis.
- To investigate the robustness of the analysis result for the primary endpoints, several sensitivity analyses will be performed. Details on these analyses will be provided in SAP

20 Ethics and Protection of Human Subjects

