## 6. Sample Size Justification

- **Primary Safety Endpoint:**

Based on a performance goal of 12% and assuming an anticipated primary safety event rate of 5% for the primary safety endpoint, a sample size of 135 subjects (with 5% missing data due to attrition) will provide above 80% power to reject the null hypothesis for the primary safety hypothesis test using a one-sided exact binomial test. The target significance level is 0.025.

- **Primary Effectiveness Endpoint:**

Based on a performance goal of 90% and assuming an anticipated failure-free rate of 97% for the primary effectiveness endpoint, a sample size of 100 subjects will provide

more than 80% power to reject the null hypothesis for the primary effectiveness endpoint using a one-sided exact binomial test. The target significance level is 0.025.

- **Secondary Effectiveness Endpoint:**

Based on a performance goal of 50% and assuming an anticipated failure-free rate of 65% for the secondary effectiveness endpoint, a sample size of 100 subjects (with 10% missing data due to attrition) will provide above 80% power to reject the null hypothesis test for the secondary effectiveness hypothesis using a one-sided exact binomial test. The target significance level is 0.025.

- **Total Sample size:**

The sample size of this study is mainly driven by the hypothesis test for the primary safety endpoint. The total sample size for this study will be 135 subjects, based on the 135 subjects needed for the primary safety endpoint evaluation, 100 subjects for the primary acute effectiveness endpoint evaluation, and 100 subjects for the secondary effectiveness endpoint evaluation. The sample size estimation assumes a 5% attrition rate of the subjects for the primary safety endpoint and no and 10% attribution of the subjects for the primary and secondary effectiveness endpoints, respectively.

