### 7.6.2 Primary Effectiveness Endpoint

- **Sensitivity to Analysis Set**

The hypothesis testing will be performed in the mITT analysis set for the acute effectiveness endpoint.

- **Best-case Scenario**

Subjects with missing acute effectiveness outcome data will be treated as a success in this analysis. The proportion of subjects who are acute effectiveness success will be estimated in the PP and mITT analysis sets.

- **Worst-case Scenario**

Subjects with missing acute effectiveness outcome data will be treated as a failure in this analysis. The proportion of subjects who are acute effectiveness success will be estimated in the PP and mITT analysis sets.

- **Tipping Point Analysis**

Tipping point analysis will be performed for the acute effectiveness endpoint to assess the impact of missing outcomes on the effectiveness conclusion. The proportion of subjects with acute effectiveness success will be updated one by one by incrementally treating a subject with a missing outcome as failure to evaluate whether a tipping point is identified. If the lower bound of the exact two-sided 95% confidence interval of an acute effectiveness success rate is less than the performance goal of 90%, then the tipping point is considered identified. Otherwise, no tipping point is found. The analysis will be performed in the PP and mITT analysis sets.

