### **7.8.3 Secondary Effectiveness Endpoint**

For the secondary effectiveness endpoint analysis, if a subject has an effectiveness failure at any time during the effectiveness evaluation period (Day 91-365), then the subject will be considered to have an event. Subjects who do not experience an effectiveness failure and do not have a full 12-month follow-up and/or sufficient follow-up duration for the secondary effectiveness endpoint (i.e., with at least 335 days of follow-up and arrhythmia monitoring post the index procedure) will be considered missing outcome for the secondary endpoint. These subjects will be censored on the date of their last follow-up for the Kaplan-Meier analysis.

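### The 12-month endpoint is decided on a confidence bound, but its worst-case missing-data check is a bare point estimate that, at the planned 10% loss, stays above 50% after every pass

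*SAP*

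**What the plan says.** SAP 7.10 has the secondary endpoint "evaluated using the exact test for a binomial proportion at a one-sided significance level of 2.5" per cent, in the PP set. The endpoint is met if the "lower bound of the exact two-sided 95% confidence interval of the 12-Month effectiveness success rate is greater than the performance goal of 50" per cent.

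SAP 7.8.3 sets out who is counted. A failure at any time in Day 91-365 is an event, however long the subject was followed. An event-free subject without at least 335 days of follow-up and arrhythmia monitoring "will be considered missing outcome for the secondary endpoint". Protocol 19.4.6.1 has the same asymmetry: "Subjects without an effectiveness failure who do not have full 12 months of follow-up will be excluded from the final effectiveness analysis".

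SAP 7.10 adds an mITT analysis, Kaplan-Meier curves in PP and mITT (censoring at last follow-up under SAP 7.8.3), a best case and a worst case. On the worst case it says only: "The point estimate for freedom from secondary effectiveness failure will be estimated by treating subjects with missing secondary effectiveness outcomes as failures". No interval, criterion or analysis set is given.

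SAP 7.6 restricts its sensitivity analyses to the primary endpoints. Both of those have a tipping-point analysis. For acute effectiveness (SAP 7.6.2) the success rate is "updated one by one by incrementally treating a subject with a missing outcome as failure", and the exact lower bound is compared with the goal each time, in PP and mITT.

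SAP 6 plans for 5% loss on safety, none on acute effectiveness and 10% on the 12-month endpoint.

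**The concern.** The hypothesis-tested endpoint with the largest planned loss has the weakest missing-data check. The claim is decided on a lower confidence bound, while the analysis meant to stress it yields a number on another scale. A reader who sees a worst case of, say, 54% beside a goal of 50% may conclude that the result withstands the missing data, when the same worst case judged by the SAP's own criterion would not pass.

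This is the trial's only formal test of 12-month effectiveness, which the protocol summary lists within the major objective. At stake is whether the Final CSR can say how far that conclusion depends on subjects whose outcome is unknown. The direction of any bias cannot be known in advance, so the check should be able to reveal it.

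**Working it through.** **Inputs.** One-sided exact binomial test at 0.025 and goal 50% (SAP 7.10). Assumed rate 65%; 100 subjects with 10% missing; total 135 (SAP 6). Ten per cent missing leaves 90 of 100, or 121 of 135 (14 lost). The 135-subject figures assume that all enrolled subjects would otherwise be in the analysis.

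**1. The plan's own figure.** SAP 6 states: "Based on a performance goal of 50% and assuming an anticipated failure-free rate of 65% for the secondary effectiveness endpoint", 100 subjects with 10% missing give power above 80%. For n = 90 the smallest r with P(X ≥ r | 90, 0.50) ≤ 0.025 is r = 55 (P = 0.0223). Power is P(X ≥ 55 | 90, 0.65) = 81.2%. The statement is reproduced.

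**2. Smallest worst-case estimate compatible with a pass.** This is the smallest passing count divided by all subjects, missing ones included.

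| Subjects | Missing | Smallest pass | Worst-case estimate | Worst-case exact lower bound |
|---|---|---|---|---|
| 100 | 10 | 55/90 | 55/100 = 55.0% | 44.7% |
| 135 | 14 | 72/121 | 72/135 = 53.3% | 44.6% |

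At 10% loss no pass can have a worst-case estimate at or below 50%. That first becomes possible at 19 missing of 100 (50/81 passes; 50/100 = 50.0%) or 23 missing of 135 (67/112 passes; 67/135 = 49.6%), which is 19% or 17% loss.

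**3. The same worst case judged on the bound.** With missing subjects as failures, a lower bound above 50% needs 61/100 or 80/135.

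- 100 subjects: 55 to 60 of 90 pass the test but not the worst case. P(55 ≤ X ≤ 60 | 90, 0.65) = 48%.
- 135 subjects: 72 to 79 of 121 pass the test, with worst-case lower bounds of 44.6% to 49.7%. P(72 ≤ X ≤ 79 | 121, 0.65) = 47%, out of a total pass probability of 91.2%.

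A result close to expectation, 79/121 = 65.3%, has a worst case of 79/135 = 58.5% with lower bound 49.7%.

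**4. What a tipping point would show.** Starting from 121 analysed and 14 missing, count missing subjects as failures one at a time until the lower bound is no longer above 50%:

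| Successes of 121 | Missing counted as failures at the tip |
|---|---|
| 72 | 1 |
| 74 | 5 |
| 76 | 8 |
| 79 | 14 |

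Results that need 1 and 14 such failures differ greatly in robustness, yet their worst-case estimates (53.3% and 58.5%) both simply read as above 50%.

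**5. Direction and size of the bias.** Assume 135 treated, 10% lost, a true rate of exactly 50%, and a goal that applies to all treated subjects. Let q be the later failure rate of those lost. The success rate among those counted is s = (0.5 − 0.1(1 − q))/0.9, and the false-positive rate is P(X ≥ 72 | 121, s).

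| q | s | False-positive rate |
|---|---|---|
| 25% | 0.472 | 0.4% |
| 40% | 0.489 | 1.2% |
| 50% | 0.500 | 2.3% |
| 75% | 0.528 | 8.2% |
| 100% | 0.556 | 21.7% |

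If dropout is unrelated to outcome, the exclusion works against the device, because early failures among dropouts count while their event-free time does not. Illustration, assuming 10% drop out evenly over Day 91-365 and a constant hazard: at a true rate of 50%, a fraction (1 − 0.5)/ln 2 = 0.721 of dropouts leave event-free. The observed rate is 0.45/(0.9 + 0.1 × 0.279) = 48.5%, and those lost event-free would later fail in 1 − 0.5/0.721 = 31% of cases. A true 65% is observed as about 63.7%.

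**The case against.** **Other checks are planned.** This is correct: the worst case is not alone. Kaplan-Meier uses the partial follow-up of the excluded subjects, and the mITT analysis widens the set. But Kaplan-Meier censoring assumes that those who leave resemble those who stay, and mITT changes who is included, not how missing outcomes are treated. Neither counts missing subjects as failures.

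**The primary endpoints' best and worst cases are also only estimates.** This stands. The real difference is the tipping-point analysis, which the secondary endpoint lacks. The exact bound could also be worked out from a reported worst-case count and denominator, so nothing is concealed.

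**No commitment is broken.** Protocol 19.4.6.1 promises sensitivity analyses for the primary endpoints only, and study success rests on those two. This limits the weight of the point.

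Four stronger readings are tempting, and the documents do not support them.

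- *The exclusion inflates the success rate.* It does so only if those lost would later fail more often than 50% when the true rate is at the goal. The documents give no reason to expect 75% to 100%, and uninformative dropout pushes the other way.
- *The goal and the test describe different populations.* Protocol 5.3 calls the goal "based on the minimum chronic acceptable success rate for paroxysmal AF at 12-month follow-up", and the trial enrols paroxysmal AF. Whether the source meant all treated patients or completers cannot be seen from these documents. The false-positive figures assume the former.
- *The worst case can never contradict a pass.* This ends at about 17% to 19% loss, and it treats 50% as the yardstick for an estimate for which the SAP sets none.
- *A result that fails the worst case has failed the endpoint.* The criterion applies to subjects with a known outcome. Counting every lost subject as a failure is a deliberate extreme.

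**Conclusion.** The point holds as a gap in the sensitivity analysis. The main test is sound as specified and its stated power is reproduced. At the planned 10% loss, however, the worst-case estimate is above 50% after every pass, while roughly half of trials at the assumed 65% would pass with a worst-case lower bound below 50%. As written, the check cannot separate a conclusion that one missing failure would overturn from one that needs 14.

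The cut-offs and zones follow from the exact test and rest on 10% loss from 100 or 135 subjects. PP exclusions and those in SAP 7.1.3 would change the denominators. The false-positive rates also rest on the reading of the goal and on hypothetical later failure rates. They show that the bias can go either way and do not predict its size here. The change is worth making before the 12-month data are seen, but study success does not depend on it.

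**What to change.** In SAP 7.10:

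1. Report the best and worst cases with the exact two-sided 95% interval, and state whether each lower bound exceeds 50%.
2. Add the tipping-point analysis of SAP 7.6.2 for the secondary endpoint, counting missing subjects as failures one at a time until the lower bound is no longer above 50%.
3. Run both in the PP and mITT sets, naming them.
4. Report the tipping number beside the 12-month conclusion in the Final CSR, with a sentence saying that the worst case measures sensitivity and does not replace the main test.

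The main test, its criterion, the significance level and the sample size stay unchanged. The cost is a few lines of SAP text and reuse of programming already planned for the primary endpoints, with no new data, subjects or visits. The downside for the sponsor is that the 12-month claim may be shown to be sensitive to loss to follow-up.

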## **7.11 Additional Endpoint Analyses**

No formal statistical hypothesis will be formulated and performed for the additional endpoints. Descriptive statistics will be provided on all additional endpoints in the analysis sets specified below.

### **7.11.1 Additional Procedural Endpoints**

The analyses for the additional procedural data will be summarized descriptively in the mITT and PP analysis sets:

### **7.11.2 Additional Safety Endpoints**

The analyses for the additional safety endpoints, including SADEs, UADEs and USADEs, SAEs, and non-SAEs, will be summarized descriptively in SP and mITT analysis sets as the total number of events, number of subjects with events, and percentage of subjects with events. The SAEs and non-SAEs will be summarized overall and by timepoints of 7 days (early-onset), 8-30 days (peri-procedural), and >30 days (late onset) of initial ablation procedure.

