7.3.4 Additional Safety Endpoints

Safety

- Incidence of Serious Adverse Device Effects (SADEs)
- Incidence of Unanticipated (Serious) Adverse Device Effects (UADEs and USADEs)
- Incidence of Serious Adverse Events (SAEs) within 7 days (early-onset), 8 to 30 days (peri-procedural) and >30 days (late onset) of index ablation procedure
- Incidence of non-serious adverse events (non-SAEs)

Neurological Assessment Subset

- Occurrence, anatomical location and size of new post-ablation asymptomatic and symptomatic cerebral emboli observed post-ablation as determined by Magnetic Resonance Imaging (MRI) evaluations
- Incidence of new or worsening neurological deficits post-ablation and at follow-up, compared to baseline
- Summary of Mini Mental State Examination (MMSE), National Institute of Health Stroke Scale (NIHSS) and Modified Rankin Scale (mRS) at baseline, post-ablation and during follow-up (if lesions were identified in prior evaluation)

CT/MRA Subset

- Occurrence of PV stenosis up to 3 months post-ablation as determined by Computed Tomography (CT)/ Magnetic Resonance Angiogram (MRA) evaluations.

Esophageal Endoscopy Subset

- Occurrence of endoscopically detected esophageal thermal lesions in the region of the contact area between esophagus and LA as determined by post procedure endoscopy.

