13.4 Repeat Ablation Procedures

Repeat procedures may be performed at the discretion of the investigator. It is highly recommended to collect arrhythmia documentation (in example documented recurrences) before performing a repeat procedure.

Repeat procedures **during the blanking period** (\leq 90 days post index ablation procedure) must be conducted with the investigational device, with or without focal touch-up, if the arrhythmia is due to PV triggers. If the arrhythmia is due to non-PV triggers and the subject is treated with a commercially available ablation catheter and generator, the subject will be excluded from the long- term effectiveness cohort. Procedures for CTI dependent flutter in the follow up period are not considered repeat procedures per CIP.

Repeat procedures performed **after the blanking period** (\geq 90- 365days post index ablation procedure) may be managed per investigator discretion using a commercially available ablation catheter and generator.

For the repeat procedures, the investigator must collect and provide information on location of reconnections of PVs and in case of atrial flutter recurrence, confirm if CTI dependent flutter or not. The follow-up schedule will remain based on the index ablation procedure.

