13.5 Post-Ablation Follow-up Schedule

The subjects will be required to complete follow-up visits through 12 months post index ablation procedure. Follow-up will be done at 7 days (phone call or clinic visit), 1, 3, 6 and 12 months (clinic visit). Follow-up visits should be scheduled according to the following timeframes: 1 month (1M 23-37), 3 months (3M, day 76-104), 6 months (6M, day 166-194) and 12 months (12M, day 335-379). Follow-up visit schedule should be based on the date of the index ablation procedure and will not reset if subject undergoes a repeat AF ablation procedure.

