- A repeat electro anatomical creation of a paced activation map and bipolar voltage map will be performed by the ablating physician* in the enrolling hospital at 75 days (+/-15days) post index ablation procedure to verify isolation durability of the treated pulmonary vein during the index ablation procedure.
- A BWI multi-electrode mapping catheter should be used for the remap procedure. It is **REQUIRED** to use the same mapping catheter that was used during the index ablation procedure.
- Additional ablations may be performed at the discretion of the investigator.
- **NOTE***: preference to have the PVI durability assessment performed by the same ablation physician that treated the subject during index ablation procedure.

- **Quality of life** via the Atrial Fibrillation Effect on Quality-of-Life (AFEQT™) questionnaire (non-SOC), at Month 3, 6 and 12. **NOTE:** Patient questionnaires will only be used in countries with validated languages.

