13.7 Unscheduled Visit

If a subject returns for a potential study related cardiovascular or neurological visit outside of the CIP -defined visit schedule provided in Table 3, the visit will be considered “unscheduled” (UNS). An investigator may request an unscheduled visit in the presence of a new or worsened cardiovascular condition or neurological deficit. If the unscheduled visit is for a repeat ablation procedure, the CIP follow-up schedule is based on the index ablation procedure. For all unscheduled visits, an unscheduled visit eCRF must be completed and the subject must also return for their next scheduled study visit per clinical investigational plan.

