14.1.3 Primary Adverse Event

A **Primary Adverse Event** is an event listed in Table 5 which occurs within the first week (7days) following the study index ablation procedure.

Table 4: Primary Adverse Events

Primary Adverse Event	Description / Criteria
Death ¹	Subject death directly related to the device or procedure and occurs at any time during or after the procedure.
Atrio-Esophageal Fistula ¹	Defined as a connection between the atrium and the lumen of the esophagus. Evidence supporting this diagnosis includes documentation of esophagus erosion combined with evidence of a fistulous connection to the atrium such as air emboli, an embolic event, or direct observation at the time of surgical repair. A CT or MRI scan is the most common method of documentation of an AEF.
Myocardial Infarction	Presence of any one of the following criteria: 
- Detection of ECG changes indicative of new ischemia (new ST-T changes or new Left Bundle Branch Block [LBBB]) that persist for more than 1 hour- Development of new pathological Q waves on ECG- Imaging evidence of new loss of viable myocardium or new regional wall motion abnormality
Cardiac Tamponade ² /Perforation	The development of a significant pericardial effusion during or within 30 days of undergoing the index AF ablation procedure. A significant pericardial effusion is one that results in hemodynamic compromise, requires elective or urgent pericardiocentesis, or results in a 1cm or more pericardial effusion as documented by echocardiography Cardiac tamponade/perforation should also be classified as: 
• Early – diagnosed prior to discharge• Late – following initial discharge from the hospital
Thromboembolism	Formation of a clot (thrombus) inside a blood vessel causing obstruction to blood flow accompanied by clinical symptoms. The thrombus can migrate (embolus) and obstruct distal vascular sites. Diagnostic tests to help detect thromboembolisms may include but are not limited to angiography (pulmonary or distal), ventilation-perfusion (V/Q) scans, venography, Doppler ultrasonography, spiral CT, and echocardiography. For the purpose of this study silent (asymptomatic) cerebral embolism will not be considered a PAE.

Primary Adverse Event	Description / Criteria

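### Adverse-event windows run only from the index ablation, so acute complications of the Day 60–90 remap, and of repeat study-device ablations after Day 30, are tabulated as late onset

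*SAP*

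**What the plan says.** **Event classes.** SAP 7.11.2 summarises SAEs and non-SAEs overall and by window, the later windows being "8-30 days (peri-procedural), and >30 days (late onset) of initial ablation procedure". SAP 7.4.4.2 uses the same anchor for SAEs. Protocol 7.3.4 lists "Incidence of Serious Adverse Events (SAEs) within 7 days (early-onset), 8 to 30 days (peri-procedural) and >30 days (late onset) of index ablation procedure".

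**Primary adverse events (PAEs).** Protocol 14.1.3 defines a PAE as a listed event "which occurs within the first week (7days) following the study index ablation procedure". For device- or procedure-related death, pulmonary vein stenosis and atrio-esophageal fistula, the footnotes to Protocol 7.3.1 and Table 4 extend the window to 90 days. Those footnotes say only *post-procedure*, without naming the procedure.

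**Later procedures.** Under Protocol 13.4, repeats in blanking "must be conducted with the investigational device, with or without focal touch-up, if the arrhythmia is due to PV triggers". Under Protocol 7.2.4 and 13.5.2, 30 subjects have a remap at 75 ± 15 days, marked as outside standard of care. There, "Additional ablations may be performed at the discretion of the investigator".

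**Follow-up clock.** Protocol 13.5 says the visit schedule "will not reset if subject undergoes a repeat AF ablation procedure". Protocol 13.7 adds: "If the unscheduled visit is for a repeat ablation procedure, the CIP follow-up schedule is based on the index ablation procedure".

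**What counts as a repeat.** Under SAP 7.1.4, ablation at the remap without AF, AT or AFL is not reported as a repeat procedure.

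**The concern.** A class named late onset will be read as delayed harm from the index ablation. Here it will also hold tamponades, strokes or groin bleeds from the day of a second procedure. For the remap, that procedure exists only because of the study. A reader of the report could not tell the two kinds of event apart. Nor could a reader find the acute safety of repeat use of the investigational system, or of the remap, in any table. The unclear 90-day clock matters for a different reason: it bears on the primary safety count, which SAP 7.5 treats as final in the 3-month report.

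**Working it through.** **1. The plan's own figure.** Inputs (SAP 6): performance goal 12%, assumed rate 5%, N = 135 with 5% attrition, one-sided 0.025, exact binomial.
- n = 135 × 0.95 = 128.25, taken as 128.
- The largest c with P(X ≤ c | 128, 0.12) ≤ 0.025 is c = 8 (attained level 0.0240).
- Power = P(X ≤ 8 | 128, 0.05) = 80.8%.

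The stated power above 80% is reproduced. The event classes at issue do not enter it.

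**2. Remap.** The window is 75 − 15 = Day 60 to 75 + 15 = Day 90. A complication on or after the remap has an index day of at least 60. Since 60 > 30 it is always late onset, and since 60 > 7 it is always outside the 7-day PAE window.

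**3. Repeat ablation.** A complication k days after a repeat on Day d is filed under index Day d + k. Examples:

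| Repeat (d) | Complication (k) | Index day | Class |
|---|---|---|---|
| 5 | 1 | 6 | early-onset, inside the PAE window |
| 20 | 1 | 21 | peri-procedural |
| 28 | 4 | 32 | late onset |
| 60 | 0 | 60 | late onset |

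The late-onset label is certain for repeats after Day 30. For earlier repeats it depends on the index day.

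**4. The 90-day rule under two readings.**
- From the index: a remap on Day 60 / 75 / 90 leaves 90 − 60 = 30, 90 − 75 = 15, or 90 − 90 = 0 days of window.
- From the later procedure: the window closes on index Day 150 / 165 / 180, after the last permitted 3-month visit (Day 104). For late-enrolled subjects it could still be open at the primary analysis.

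That timing fits the index reading better, but neither document states it. SAP 7.8.1 counts a PAE whatever the length of follow-up, which does not settle the clock.

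**5. Planned outputs.**
- SAP 7.11.2: SAEs and non-SAEs overall and by index window; SADEs and UADEs/USADEs without a window. Nothing is split by procedure.
- SAP 7.11.3: counts of repeats, reconnections and non-PV targets. No adverse events.
- SAP 7.12.1: durability percentages. No adverse events.
- SAP 7.1.4: some remap ablations are absent from the repeat tables as well.

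**6. Size.** Planned remaps: 30/135 = 22.2%. The number of repeats is not given. The documents give no complication rate for a remap, so the rates here are assumptions.
- At 1% / 3% / 5%, expected events are 30q = 0.3 / 0.9 / 1.5, and P(at least one) = 1 − (1 − q)^30 = 26% / 60% / 79%.
- Protocol Table 8 gives AF-ablation rates for tamponade (0.2–5%), vascular complications (0.2–1.5%) and stroke/TIA (0–2%). They sum to 0.4–8.5%, or 0.12–2.55 events in 30. The upper end adds three upper limits and borrows ablation rates for what may be mapping only.

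**7. Precision of a separate remap row.** For 0/30 the exact two-sided 95% upper bound is 1 − 0.025^(1/30) = 11.6%. For 1/30 it is 17.2%.

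**The case against.** Index anchoring of the 7-day window and the event classes is explicit and consistent across both documents, and an index-only primary endpoint is a legitimate choice. The additional safety analyses are descriptive. The additional objective (Protocol 6.2) concerns SAE incidence up to 12 months, which the overall row serves; SADEs carry no window. All of this stands, and it confines the point to labelling.

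A reader might go further in five ways that the documents do not support:
- *The events are lost.* Complications of re-ablation are expressly AEs (Protocol 14.1.1), AEs are collected to study end (14.4.1), SAEs are due within 72 hours (Table 9), and all study-device failures are reportable (14.4.4).
- *Every repeat complication becomes late onset.* Not before Day 31 (step 3).
- *A fistula on Day 100 after a Day 75 re-ablation is definitely excluded from the PAEs.* The 90-day wording is ambiguous, not exclusionary.
- *There is no contact after these procedures.* Regular visits continue; on nominal dates the 3-month visit falls 90 − 75 = 15 days after the remap. Only a contact tied to the later procedure is unspecified. If the 3-month visit comes first, the next scheduled visit is 166 − 90 = 76 to 194 − 77 = 117 days after the remap, but that needs an early visit and a later remap.
- *These events belong in the primary count.* Adding remap events at the assumed 1% / 3% / 5%, with the limit of 8 in 128 unchanged, would cut power from 80.8% to about 77% / 69% / 61% and change the question being tested.

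**Conclusion.** The point holds as a classification fault in the secondary safety tables. It is certain for the remap and for repeat study-device ablations after Day 30, and absent or partial for earlier repeats. No stated figure is wrong and the primary test is unaffected. The number of events is likely to be small: about 0.3 to 1.5 among 30 remaps at assumed rates of 1–5%, plus an unknown number from repeats. It assumes that all 30 remaps take place, although discontinued subset subjects skip them. The ambiguity in the 90-day rule is separate. It could affect the primary count only in the rare case of one of the three named events after a second procedure, but it should be settled before the data are seen. This is an inexpensive improvement, not a threat to the trial's conclusions.

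**What to change.** 1. Keep the primary endpoint on the index procedure.
2. In SAP 7.11.2 and Protocol 7.3.4, add a descriptive table of SAEs and PAE-type events by days since the most recent study procedure, with index, repeat ablation and remap shown separately. Define *study procedure* so that remaps with ablation but no documented arrhythmia, which SAP 7.1.4 does not count as repeats, are included. The table describes timing and does not assign cause, so it should supplement the index-based one.
3. In the existing late-onset row, footnote or separate the events that followed a repeat or remap.
4. In Protocol 7.3.1 and Table 4, state which procedure *post-procedure* and *procedure related* refer to, before the 3-month analysis.
5. The sponsor should reconcile Protocol 13.3.6, 13.4, 13.5.2 and 13.7 on which assessments apply after a repeat or remap. No schedule is proposed here.

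Cost: one table and one procedure-date variable. The remap row will be imprecise (upper bound 11.6% even with no events), so it offers transparent counts rather than a firm rate. The primary test stays at 8 events in 128 with 80.8% power.
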